#### **Statistical Method**

#### **Analysis Set**

Statistical analysis is performed using full analysis set (FAS), per-protocol set (PPS) and safety set (SS).

FAS: it includes all subjects who have received at least one dose of the investigational drug and have measurable tumors at baseline.

PPS: it includes subjects with at least one post-treatment imaging assessment of tumors, good compliance, and no serious violation or deviation against the study protocol in FAS population.

SS: it includes subjects who have received at least one dose of the investigational drug and undergone safety assessment.

#### Sample Size Determination

During phase I dose escalation study of MGD013 monotherapy, the starting dose of MGD013 will be 120 mg Q2W in one subject which has been enrolled in the group. The subsequent dose groups will adopt traditional 3+3 dose escalation scheme , with 3 - 6 evaluable subjects in each group; during dose escalation study of combination therapy, the traditional 3+3 dose escalation scheme will be used, and it is expected to have 30 - 43 subjects in total in Phase I.

There will be two cohorts in Phase II Part 1. Subjects who have previously received and not received immune checkpoint inhibitor treatment will be administered with MGD013 monotherapy or MGD013 in combination with brivanib alaninate. The SWOG two-stage design will be employed.

30 subjects are needed

There are two

stages in this part. In the first stage, if response (according to RECIST 1.1 criteria) is observed radiologically in 1 or more out of 15 evaluable subjects, the

enrollment of second stage will be open and an additional of 15 evaluable subjects will be enrolled.

40 subjects are needed

Similarly, there are 2 stages for the cohort. At least response of 3 out of 20 evaluable subjects at the first stage will support the decision to proceed to the second stage of subject accrual till there are 40 evaluable subjects in this cohort. Each cohort will have 70 evaluable subjects. Considering 10% dropout rate, up to 158 subjects will be enrolled.

According to safety and efficacy data of Phase II Part 1, a study treatment (MGD013 monotherapy or MGD013 in combination with brivanib alaninate) will be selected for Part 2 dose expansion in subjects who have previously received immune checkpoints inhibitor treatment. It is estimated to enroll 120 subjects for further assessment of its efficacy and safety.

#### **Statistical Analysis Method**

#### Safety Analysis

Safety analysis is performed in the SS population. Safety parameters include physical examination, vital signs, AEs and laboratory tests, ECG, etc. AEs will be coded using the most updated MedDRA System Organ Class and Preferred Term.

The incidence and severity of AEs, dose-limiting toxicity (DLT, phase I study), AEs leading to withdrawal from study, AEs leading to drug discontinuation, AEs leading to death, and serious adverse events (SAEs)will be summarized.

For laboratory parameters and ECG, the change during the study will be summarized by descriptive analysis. The normal and abnormal laboratory values before and after treatment will be summarized using a shift table based on the lab normal range. Listing of data will be also provided. Some specified parameters will be summarized descriptively per protocol.

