#### Hyponatremia

Approximately one third of subjects treated with brivanib alaninate were reported with hyponatremia  $\geq$  CTCAE Grade 1. CTCAE Grade 4 hyponatremia (Na  $\leq$  120 mEq/L) occurred in 4% of subjects. The severity of hyponatremia is related to the degree of hepatic impairment in patients with cirrhosis.

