    - Transaminases increased  $> 8 \times$  the upper limit of normal (ULN);
    - Grade 3 elevated total bilirubin ( $> 5 \times ULN$ );
    - Transaminases increased (5 × ULN to 8 × ULN) that does not resolve to Grade 2 within 7 days and Grade 1 or baseline within 14 days. Oral steroids must be tapered to ≤ 10 mg of prednisone or equivalent dose within 14 days.
    - Increased total bilirubin (3× ULN to 5× ULN) that does not resolve to Grade 2 within 7 days and Grade 1 or baseline within 14 days. Oral steroids must be tapered to ≤ 10 mg of prednisone or equivalent dose within 14 days.
  - For subjects with Grade 2 baseline transaminases increased (3 × ULN to 5 × ULN), the DLT is defined as:
    - Elevation of one or more transaminases (> 10 × ULN) with increased total bilirubin (≥ 1 grade, for example: Grade 0 to 1, or Grade 1 to 2);
    - Elevation of one or more transaminases (> 10 × ULN) that does not recover to Grade 2 with steroids within 14 days or that requires another immunosuppressive agent.
    - Elevation of one or more transaminases ( $> 15 \times ULN$ );
    - Grade 3 increased total bilirubin ( $> 5 \times ULN$ ).
- Any other adverse events which in the judgment of the investigator required discontinuation from the study.

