- 10. Subjects with chronic HBV infection must have HBV-DNA <500 IU/ml, and have received at least 14 days of anti-HBV treatment (e.g. entecavir, tenofovir) prior to the initiation of study treatment and are willing to receive antiviral treatment throughout the study; Antiviral therapy is not required for patients with HCV infection and the elevation of their liver enzymes must not exceed the level of CTCAE Grade 1;
- 11. Adequate organ function as outlined below:
  - (1) Blood system function (subjects must have not received blood transfusion or stimulating growth factors within 14 days prior to screening test): neutrophil count  $\geq 1.5 \times 10^9 / L$ , platelet count  $\geq 75 \times 10^9 / L$ , hemoglobin  $\geq 90 \text{ g/L}$ ;
  - (2) Liver and kidney function (no albumin transfusion within 14 days prior to

screening test): serum total bilirubin  $\leq 2.5 \times \text{ULN}$ , serum albumin  $\geq 29 \text{ g/L}$ , ALT and AST  $\leq 5 \times \text{ULN}$ ; serum creatinine  $\leq 1.5 \times \text{ULN}$  or eGFR (Cockcroft-Gault formula)  $\geq 60 \text{ ml/min}$ ;

- (3) Coagulation function: international normalized ratio (INR) $\leq$ 2.3 or prothrombin time (PT) of  $\leq$  6 seconds above control;
- (4) Left ventricular ejection fraction (LVEF) ≥50% by two-dimensional echocardiography.
- 12. Female subjects (except for females who have underwent surgical sterilization and those have been menopausal for more than one year) who are of childbearing potential are required to adopt a medically acceptable contraceptive measure (such as intrauterine device, contraceptive pill or condom) throughout the study and up to 120 days after the last dose of investigational products; females must have negative serum or urine HCG tests within 7 days prior to enrollment; female subjects must not be breastfeeding; male subjects whose partners are of childbearing potential should use effective contraceptive methods throughout the study and up to 120 days after the last dose of investigational product.
- 13. Subjects who are willing to provide oncological tissues (if applicable) for biomarker test.

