  - (2) Unstable angina pectoris or newly diagnosed angina pectoris or myocardial infarction within 12 months prior to screening;
  - (3) Arrhythmias requiring medications other than  $\beta$ -blockers;
  - (4) Valvular heart disease of  $\geq$  CTCAE Grade 2;
  - (5) Hypertension inadequately controlled by drugs (systolic pressure >150 mmHg or diastolic pressure >90 mmHg);
- 11. Subjects who have history of symptomatic pulmonary fibrosis, interstitial pneumonitis, pneumoconiosis, radiation pneumonitis, drug-related pneumonitis, or severe impairment of pulmonary function, or other suspicious pulmonary diseases that may interfere with drug-related pulmonary toxicity detection and treatment
- 12. Subjects who have suffered active bacterial or fungal infections requiring systematic treatment within 7 days prior to screening; or active tuberculosis;
- 13. Subjects with active co-infection of Hepatitis B and C, confirmed by positive HBV surface antigen or HBV DNA and HCV RNA;
- 14. Subjects who have any active, known or suspected autoimmune disease
- 15. Subjects with a condition requiring systematic treatment with corticosteroids (>10 mg/day prednisone or equivalent) or other immunosuppressive drugs within 14 days before administration of the investigational drug. In the absence of active autoimmune diseases, inhalation or topical use of steroids (>10 mg/day prednisone or equivalent) is allowed;
- 16. Other laboratory abnormalities:
  - (1) Hyponatremia, hypokalemia or hypophosphatemia that have occurred before the first administration, and failed to restore to normal level after electrolyte supplementation therapy;
  - (2) Confirmed diagnosis of thyroid dysfunction, which cannot be maintained within normal range following thyroid hormone replacement therapy;
  - (3) Positive Human immunodeficiency virus (HIV) test;
- 17. QTc interval >480 ms on two consecutive ECGs;
- 18. Female subjects during pregnancy or lactation; female subjects of childbearing potential or male subjects who are not willing to use contraception or contraceptive measures

- during the study;
- 19. Subjects who have previously received two lines and above tumor immune checkpiont inhibitor treatment, mainly including anti-PD-1, anti-PD-L1 and anti-CTLA-4 antibodies, etc, or bispecific antibodies including the above targets, or received anti-LAG-3 antibody; whether subjects who have previously received other tumor immunotherapy can be enrolled should be determined by the sponsor;

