#### **Increased Total Bilirubin**

Management guidelines for subjects experiencing increased total bilirubin are as follows:

- Grade 1 increased total bilirubin No specific therapy required.
- Grade 2 increased total bilirubin Withhold MGD013 until improvement to ≤ Grade 1 or baseline.
  - Rule out viral and other etiologies. Consider imaging examinations such as ultrasound or CT scan and liver biopsy to ascertain etiology of hepatosis. Consider oral steroids.
  - If an improvement to ≤ Grade 1 does not occur within 14 days, discontinue MGD013 and begin oral steroids.
- Grade 3 increased total bilirubin withhold MGD013.

- For increased total bilirubin > 5 × ULN, permanently discontinue MGD013 and initiate IV steroids (it is suggested to use methylprednisolone 2 mg/kg/day divided twice daily).
  - If no response to corticosteroids is observed within 3 to 5 days, an additional immune suppression therapy with mycophenolate is considered.
  - Monitor liver function testing at least twice weekly (or more frequently as clinically appropriate in the judgment of the investigator) until total bilirubin has returned to Grade 1 or baseline.
- If increased total bilirubin> 3.0  $\leq$  5 × ULN:
  - Begin immediate IV steroids; it is suggested to use methylprednisolone (2 mg/kg/day divided twice daily). Consider additional immune suppression with mycophenolate for subjects who do not respond to corticosteroids within 3 to 5 days.
  - O Monitor liver function tests including total bilirubin at least twice weekly (or more frequently as clinically appropriate in the judgment of the investigator) until total bilirubin has returned to Grade 1 or baseline.
  - o If the elevation does not improve to Grade 2 within 7 days and to Grade 1 within 14 days, discontinue MGD013.
  - o Resume MGD013 if:
    - Laboratory elevations improved to ≤ Grade 2 within 7 days and improved to ≤ Grade 1 or baseline within 14 days.
    - Steroids have been tapered to ≤ 10 mg/day of prednisone or equivalent.
  - On resuming MGD013, laboratory tests of AST, ALT, and total bilirubin will be evaluated at least once per week for 3 consecutive weeks.
  - o Permanently discontinue MGD013 in the case of a second increase of total bilirubin to ≥ Grade 3.
- Grade 4 increased total bilirubin Discontinue MGD013 and treat as for Grade 3 elevation.

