## 9.3 Statistical Analysis Method

#### 9.3.1 Safety Analysis

Safety analysis is performed in the SS. Safety parameters include: physical examination, vital signs, AEs and laboratory tests, ECG, etc. AEs will be coded using MedDRA System Organ Class and Terminology.

The incidence rates and severity levels of adverse events, dose-limiting toxicity (DLT), adverse events leading to withdrawal from the study, adverse events leading to discontinuation, adverse events leading to death, and serious adverse events will be summarized. A line listing of AEs will be provided.

Each laboratory should examine the indicators and ECG, describe their changes during the study, use a cross-classification table to describe the normal and abnormal changes before and after treatment and provide a data list. Some specified parameters will be summarized descriptively per protocol.

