## 9.3.2 Efficacy Analysis

FAS and PPS are both used for efficacy analysis, and of which, PPS is the main analysis set and FAS analysis can provide supporting evidence.

Analysis method of the primary efficacy endpoint: summary of BICR-assessed objective response rate (ORR) after administration according to RECIST1.1. The secondary endpoints include investigator-assessed ORR, BICR-assessed ORR according to irRECIST, progression-free survival (PFS), time to tumor progression (TTP), disease control rate (DCR), duration of response (DoR), survival rate at fixed time points (6, 9, 12 months) and overall survival (OS).

For the objective response rate (ORR), the point estimate, p-value of one-sided test and its 95% confidence interval (95% CI) will be provided. Kaplan-Meier method was used to estimate the survival functions for time to tumor progression (TTP), progression-free survival (PFS), and overall survival (OS), respectively, and their survival curves plots, the median TTP, median PFS, Survival rate at fixed time points and their respective 95% confidence intervals (95% CI) will be provided.

See the statistical analysis plan (SAP) for the details of Statistical Analysis.

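### The only categorical laboratory table named is normal/abnormal, before versus after treatment: it hides worsening in subjects abnormal at entry, shows no severity, and leaves the after value undefined

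*Combined protocol and SAP*

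**What the plan says.** Two places describe the laboratory summaries. The synopsis (Statistical Analysis Method, Safety Analysis) states: "The normal and abnormal laboratory values before and after treatment will be summarized using a shift table based on the lab normal range". Section 9.3.1 asks the analyst to "use a cross-classification table to describe the normal and abnormal changes before and after treatment and provide a data list". Both also promise a descriptive summary of change during the study, data listings, and a descriptive summary of certain parameters that are not named. Neither mentions CTCAE grades, a worst post-baseline value or multiples of ULN for laboratory data.

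Section 9.3.2 ends with: "See the statistical analysis plan (SAP) for the details of Statistical Analysis". No separate SAP is in the text available for this review.

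Section 4.1, criterion 11, sets the entry limits: ALT and AST up to 5 x ULN, total bilirubin up to 2.5 x ULN, platelets from 75 x 10^9/L. Subjects with HCV infection are held to a tighter rule: "the elevation of their liver enzymes must not exceed the level of CTCAE Grade 1".

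Elsewhere the protocol acts on grades and ULN multiples. Under Increased Total Bilirubin, Section 8.4.1.2 says: "For increased total bilirubin > 5 × ULN, permanently discontinue MGD013 and initiate IV steroids". The transaminase guidance in the same section has a permanent stop above 8 x ULN. Section 3.1.3 sets separate hepatic DLT limits for subjects whose transaminases are already 3 to 5 x ULN at baseline.

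**The concern.** A two-state table suits a population that enters with normal values. This one may enter with abnormal liver tests and low platelets, and the separate DLT limits in Section 3.1.3 show that the authors expected this. A subject already outside the normal range can only stay abnormal or normalise, so all worsening falls in the same cell as no change. For a subject who enters normal, a trivial excursion and a severe one share a cell.

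Safety is a primary objective in every phase. The background section on brivanib lists hepatic events as an identified risk, and Section 8.4.3 says that hepatotoxicity may overlap when the two drugs are combined. Section 3.1.4 also rests the choice of regimen for about 120 subjects in Part 2 on the Part 1 safety and efficacy data taken together. A laboratory severity table by treatment group would be useful there, although no rule refers to one.

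**Working it through.** The plan gives no figure to reproduce. The check sets the table definition against the entry limits, the action lines and the visit schedule.

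**1. What a two-state table can show.** Each subject is placed by (state before, state after), where the state is normal or abnormal by the laboratory range. Take ALT in multiples of ULN:

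| Before | After | Cell | Clinical meaning |
|---|---|---|---|
| 4 | 2 | abnormal, abnormal | improved, not normalised |
| 4 | 4 | abnormal, abnormal | no change |
| 4 | above 15 | abnormal, abnormal | past a hepatic DLT limit for a 3 to 5 x ULN baseline (3.1.3) |
| normal | 1.1 | normal, abnormal | trivial |
| normal | above 8 | normal, abnormal | past the permanent-stop line (8.4.1.2) |

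Splitting abnormal into low and high would show direction. It would still not show worsening in the same direction, or severity.

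**2. Distance from the entry limit to an action line.** Inputs are Sections 4.1 and 8.4.1.2; fold-rise = action line / entry limit.

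- ALT/AST to the permanent-stop line: 8 / 5 = 1.6.
- Bilirubin to the line above which immediate IV steroids are advised: 3 / 2.5 = 1.2.
- Bilirubin to the permanent-stop line: 5 / 2.5 = 2.0.

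These are the smallest possible rises, for a subject exactly at the limit. A subject who enters at 3 x ULN for ALT needs 8 / 3 = 2.7. They show that whole action bands lie inside one cell, not how many subjects cross them. For platelets the documents give no local lower limit of normal; the point assumes that 75 x 10^9/L lies below it.

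**3. Which value is after.** Table 1 schedules post-baseline chemistry on days 8, 15, 22, 29 and 43, at end of treatment (EOT) and at safety follow-up: up to 5 + 2 = 7 results for a subject treated through cycle 4. Coagulation has the same days and EOT only: up to 5 + 1 = 6. Neither description says whether after means last, worst or EOT. If it means last, a rise past 8 x ULN that resolves on steroids can end in the normal, normal cell.

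**4. Number affected.** The count needs four quantities: subjects treated, the share abnormal at entry, the share of those who worsen, and the share of that worsening not shown by AE outputs. The documents give no baseline distribution and no basis for the last two shares, so no count follows.

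**The case against.** The strongest reply is that severity is reported by another route. Section 8.3.5 names a one-grade worsening, or an effect on dosing, as examples of reportable laboratory change. AEs are graded by CTCAE 5.0, and AE severity and AEs that lead to stopping drug are both tabulated. A value past a permanent-stop line should therefore appear with its grade. Phase I DLTs and the AESIs of Section 8.3.9 add further routes. When a diagnosis replaces a laboratory finding, the finding is kept as supporting information and the diagnosis is itself graded. The table's categories and the choice of the after value are also ordinary SAP content, and the unnamed parameters to be summarised might include graded counts.

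Most of this stands. A reader might infer that laboratory severity is reported nowhere; the documents do not support that. Nor do they support saying that the SAP lacks a graded table, since it was not available.

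What remains is narrower. A laboratory change becomes an AE only after a judgement of medical significance (8.3.5), and events attributed to tumour progression are not AEs at all (8.3.6). In liver cancer, rising bilirubin or transaminases may be attributed to progression. DLTs cover only the first 28 days of Phase I and need at least a possible relation to drug. Descriptive summaries of change do not by themselves count subjects past a threshold, and listings are not summaries.

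**Conclusion.** The point holds as a cheap improvement, worth considering. As described in the protocol, the table does not separate worsening from no change in subjects abnormal at entry, gives no severity for those normal at entry, and leaves the after value undefined. The loss is an objective check on the AE tables, one that does not pass through medical-significance judgement or attribution to progression. No endpoint, dose rule or stopping rule uses this table.

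The conclusion rests on two assumptions: that some subjects do enter abnormal, as the criteria allow, and that the SAP does not already hold a graded table.

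Three stronger readings are tempting and should not be drawn:

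- A reader might turn the brivanib background figure ("Approximately one third of subjects treated with brivanib alaninate were reported with hyponatremia", at Grade 1 or above) into a number of masked subjects. The documents do not say that those cases started from normal sodium, and enrolment to full cohort size in Part 1 depends on the first-stage response.
- A reader might take the INR limit of 2.3 as a strict entry ceiling. Section 4.1 allows a prothrombin-time criterion as an alternative.
- A reader might take 3 x ULN as the bilirubin level at which MGD013 is first withheld. Section 8.4.1.2 already withholds at Grade 2; 3 x ULN is where immediate IV steroids begin.

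**What to change.** In the synopsis Safety Analysis and in Section 9.3.1:

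- For parameters with a CTCAE grade, replace the normal/abnormal table with baseline grade versus worst post-baseline grade, by direction (high, low) and by treatment and dose group. Run it through the safety follow-up sample, or through EOT for coagulation, which has no later scheduled sample. State how a value abnormal at baseline is graded.
- Add counts of subjects whose peak ALT or AST exceeds 5, 8, 10 and 15 x ULN, and whose peak bilirubin exceeds 3 x ULN (immediate IV steroids) and 5 x ULN (permanent stop). ULN multiples avoid a labelling difference: Section 3.1.3 attaches above 5 x ULN to "Grade 3 elevated total bilirubin", while Section 8.4.1.2 also lists above 3 to 5 x ULN under Grade 3.
- Keep normal/abnormal only for parameters without a grade. Keep the descriptive summaries, listings and AE tables.
- If the SAP already holds a graded table, align the protocol text to it.

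The cost is wording in two sections and a few more tables from data already collected, with no new tests, visits or subjects. The downside is interpretive: in single-arm liver cancer cohorts, worst-grade counts mix drug toxicity with disease decline, so they must be read with the AE tables.

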#### Efficacy Analysis

FAS and PPS are both used for efficacy analysis, and of which, PPS is the main analysis set and FAS analysis can provide supporting evidence.

Primary efficacy endpoints: ORR. Secondary endpoints are PFS, TTP, DCR, DoR and OS.

For ORR, its point estimation and the p-value (1-sided) and corresponding 95% confidence interval (95% CI) of the single-arm test will be provided. For TTP, PFS and OS, Kaplan-Meier method is adopted to estimate survival function and draw survival curve. The median TTP, median PFS, total survival rate at specific time points (at 6, 9 and 12 months) and their corresponding 95% CIs will be provided.

**Study Visit Schedule and Assessments:** See Table 1

